9.3. Safety Analyses

Adverse events will be coded using the standard dictionary (MedDRA) down to the lower level term (LLT).

An overall summary table will be presented: any adverse event, any treatment emergent adverse event (TEAE), any serious adverse event (SAE), death, any grade 3 or higher adverse events from baseline to EoS.

Two periods will be defined for TEAE:

- Any adverse event which occurs or worsens from first dosing to Day 28;
- Any adverse event which occurs after Day 28.

Adverse events will be described by primary system organ class and preferred term. Numbers and percentage of subjects, and number of occurrence of adverse event will be presented for:

- TEAE;
- Serious TEAE;
- TEAE leading to drug discontinuation;
- TEAE of grade 3 or 4;
- TEAE for which relationship with the study drug is recorded as possible or probable.

The assessment of safety will be based on the frequency of adverse events (with and without regard to causality) graded according to the Division of AIDS table for grading the severity of adult and pediatric adverse events (version 2.0, November 2014) and also, the review of individual values for clinical laboratory data, vital signs and ECG focusing on the detection of abnormal values and PCSAs [potentially clinically significant abnormalities (PCSA) determined upon investigator considerations].

Adverse events will be tabulated (counts and percents) by group. All adverse events will be listed and the data will be tabulated by body system/organ class. Adverse event tabulations will include all treatment emergent adverse events, which will be further classified by severity, and relationship to treatment and dose level.

Clinical laboratory parameters, vital signs, ECG will be summarized by using descriptive statistics (n, mean, SD, SEM, median, minimum and maximum). Number of subjects with at least one abnormal values will be tabulated (counts and percents) for each parameter in summary shift tables, by group and dose.

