3. INVESTIGATIONAL PLAN

3.1. Study design

3.1.1. Design and methodology

The ABX464-005 study is a Phase Ib, sequential cohort open label trial designed to provide additional safety and compartmental PK data on ABX464.

The study will also generate exploratory immunological and virological data that combined with the compartmental PK data will help further characterize the mechanism of action of ABX464.

The study will enroll both HIV-infected (N=24) and HIV-uninfected (N=12) study subjects in three distinct cohorts:

- Cohort 1: 12 HIV-infected subjects treated with ABX464 150 mg o.d. for 28 days
- Cohort 2: 12 HIV-uninfected subjects treated with ABX464 50 mg o.d. for 28 days
- Cohort 3: 12 HIV-infected subjects treated with ABX464 50 mg o.d. for 84 days

HIV-infected subjects will add the investigational product to their current antiretroviral regimen whereas the HIV-uninfected subjects will only receive the investigational product.

Cohort 1 will consist of 12 HIV infected subjects. After full enrollment and an interim analysis (including PK and immunological markers) of Cohort 1, Cohort 2 and 3 will begin enrollment and will consist of both HIV infected (n=12) and HIV uninfected (n=12) subjects.

Subjects who successfully complete a screening visit (Visit 1) will advance to a Baseline visit (Visit 2; Day 1). During this visit all subjects will undergo a physical examination and have blood and rectal tissue samples collected.

The rectal tissue samples will be collected before initiating oral dosing with the investigational product (150 mg or 50 mg of ABX464).

After receiving the first dose of ABX464, additional blood PK samples will be collected at 0h, 0.5h, 1h, 1.5h, 2h, 4h, 6h and 8 hours.

All subjects will receive the investigational product once daily for 28 days (Cohorts 1 &2) and for 84 days (Cohort 3).

At Day 28 for subjects enrolled in cohort 3 and at the end of the treatment period (End of Rx Visit; Day 28 for Cohorts 1&2 and Day 84 for Cohort 3) subjects will undergo a physical examination and have blood and rectal tissue collected. PK blood samples will be collected at 0h, 0.5h, 1h, 1.5h, 2h, 4h, 6h and 8 hours.

HIV infected subjects will continue with their antiretroviral regimen i.e. there will be no antiretroviral treatment interruption in this study.

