5.3.2. Baseline Visit (Day 1)

- Physical examination and vital signs;
- Microbiome specimen collection (swabs);
- Hematology (incl. INR and PT if clinically indicated);
- Biochemistry;
- 12 lead ECG;
- Viral Load, CD4/CD8 count (HIV infected Subjects);
- Blood collection for HIV reservoir assessment (HIV infected Subjects) and immuno-evaluation;
- Flexible sigmoidoscopy with collection of rectal biopsies;
- Dispense study treatment to subject and instruct how to take them
- Perform PK blood samples (0h, 0.5h, 1h, 1.5h, 2h, 4h, 6h and 8 hours);
- Adverse event assessment.

5.3.3. Control Visits 3,4, & 5 (Days 7, 14, & 21)- Cohort 2

To be performed only in HIV-uninfected subjects:

- Physical examination and vital signs;
- Check Study treatment compliance;
- Adverse event assessment.

5.3.4. Day 28 Visit (\pm 2 days)- Cohort 3

To be performed only in subjects enrolled in the Cohort 3:

- Physical examination and vital signs;
- Microbiome specimen collection (swabs);
- Hematology (incl. INR and PT if clinically indicated);
- Biochemistry;
- Viral Load, CD4/CD8 count;
- Blood collection for HIV reservoir assessment and immuno-evaluation;
- Flexible sigmoidoscopy with collection of rectal biopsies;
- Perform PK blood samples (0h, 0.5h, 1h, 1.5h, 2h, 4h, 6h and 8 hours);
- Check Study treatment compliance;
- Adverse event assessment.

5.3.5. Day 56 Visit (\pm 2 days)- Cohort 3

To be performed only in subjects enrolled in the Cohort 3:

- Physical examination and vital signs;
- Hematology and Biochemistry;

- Blood collection for HIV reservoir assessment and immuno-evaluation;
- Check Study treatment compliance;
- Adverse event assessment.

5.3.6. End of study treatment visit (D28 for cohort 1&2 or D84 for cohort 3; \pm 2 days)

- Physical examination and vital signs;
- Microbiome specimen collection (swabs);
- Hematology (incl. INR and PT if clinically indicated);
- Biochemistry;
- 12 lead ECG;
- Viral Load, CD4/CD8 count (HIV infected Subjects);
- Blood collection for HIV reservoir assessment (HIV infected Subjects) and immuno-evaluation;
- Flexible sigmoidoscopy with collection of rectal biopsies;
- Perform PK blood samples (0h, 0.5h, 1h, 1.5h, 2h, 4h, 6h and 8 hours);
- Check Study treatment compliance;
- Adverse event assessment.

5.3.7. Follow-up Visit (D35 for cohort 1&2 or D91 for cohort 3; \pm 2 days)

- Physical examination and vital signs;
- Hematology (incl. INR and PT if clinically indicated);
- Biochemistry;

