### 3.4 Study Timepoints

From a subject standpoint, the study participation is defined as

- Two to four weeks of screening period;
- Four weeks (Cohorts 1 & 2) or twelve weeks (Cohort 3) as the treatment period (ABX464);
- Follow-up visits at 1 week and 4 weeks after cessation of study medication.

Overall, the minimal study duration is approximately 70 days and up to 140 days depending on the subject Cohort.

Visits and visit windows are defined as follows:

Visit	Study Day	Window
-------	-----------	--------

Screening	-21	± 7 days
Baseline	1	
Control (Cohort 2 only)	7	± 2 days
Control (Cohort 2 only)	14	± 2 days
Control (Cohort 2 only)	21	± 2 days
Day 28 (Cohort 3 only)	28	± 2 days
End of Study Treatment (Cohort 1 & 2)	28	± 2 days
Follow-up (Cohort 1 & 2)	35	± 2 days
End of Study (Cohort 1 & 2)	56	± 7 days
Day 56 (Cohort 3 only)	56	± 2 days
End of Study Treatment (Cohort 3 only)	84	± 2 days
Follow-up (Cohort 3 only)	91	± 2 days
End of Study (Cohort 3 only)	112	± 7 days

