#### 11.4.2 Laboratory Data

Routine clinical laboratory results will be carried out at screening, all visits during the treatment period. The laboratory parameters include:

- Haematology: hemoglobin, hematocrit, WBC, neutrophils, lymphocytes, monocytes, eosinophils, basophils, platelet count, INR, PT
- Biochemistry: sodium, potassium, chloride, calcium, phosphate, glucose, BUN or urea, creatinine, AST, ALT, alkaline phosphatase, total bilirubin, GLDH, total protein, lipase, albumin, LDH, gGT, CRP,

Laboratory parameters will be summarised at each visit using descriptive statistics on the SAF set. Laboratory parameters classified as normal/ abnormal non clinically significant (NCS)/ abnormal clinically significant (CS) will be presented in a shift table showing changes from baseline to each visit for patients with at least one abnormal CS value. Baseline is defined as the last non-missing value before the first dose of study drug, which is Day 0.

If laboratory results are repeated at the same visit, the repeated result will be used in summaries (instead of the original one) provided the sample was taken within the visit window, otherwise the original result will be used. All results will be listed.

Laboratory results at unscheduled visits will be included in the listings but will not be summarised.

For all female patients of childbearing potential, a blood pregnancy test ( $\beta$ -HCG) will be performed at Day 0 and then a urine pregnancy test will be performed at each visit until VR. Results of all pregnancy testing will be listed only.

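### The whole-study count of subjects with any abnormal laboratory value compares 3 scheduled draws in the 150 mg cohort with 5 in the 84-day 50 mg cohort, so it is not like-for-like

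*Protocol*

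**What the plan says.** Protocol 9.3 sets out this count, and SAP 4.4 repeats it: "subjects with at least one abnormal values will be tabulated (counts and percents) for each parameter in summary shift tables, by group and dose". The sentence covers laboratory parameters, vital signs and ECG. Neither document limits the count to visits that all cohorts share, or asks for the number of assessments behind it. Protocol 9.3 does split treatment-emergent adverse events at Day 28; laboratory values get no such split.

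Protocol 3.1.1 defines the groups:

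- The higher-dose group is "Cohort 1: 12 HIV-infected subjects treated with ABX464 150 mg o.d. for 28 days".
- The lower-dose group without HIV infection is "Cohort 2: 12 HIV-uninfected subjects treated with ABX464 50 mg o.d. for 28 days".
- The lower-dose group with the longer treatment is "Cohort 3: 12 HIV-infected subjects treated with ABX464 50 mg o.d. for 84 days".

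SAP 10.1 gives each cohort its own column. On laboratory data, SAP 11.4.2 adds: "Laboratory results at unscheduled visits will be included in the listings but will not be summarised". Protocol 9.3.1 and SAP 11.4.2 also plan descriptive laboratory statistics at each visit. SAP 11.4.2 adds a shift table from baseline to each visit, restricted to patients who have at least one clinically significant (CS) abnormal value.

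**The concern.** The chance that a subject has at least one abnormal value rises with the number of times the subject is measured. If one cohort is drawn more often than another, its count is expected to be higher even when the risk at each draw is the same. Here the cohort with most draws is also the one with the longest treatment. A difference between the Cohort 1 and Cohort 3 columns could therefore reflect dose, duration or number of draws, and the table cannot separate them. Cohorts 1 and 3 are the two HIV-infected groups, so this is the pair a reader would most naturally use to compare 150 mg with 50 mg.

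**Working it through.** The plan states no figure to reproduce: there is no sample size calculation and no expected abnormality rate.

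**Step 1. Count the scheduled draws.** The source is the visit lists in protocol 5.3.2 to 5.3.8. The section 5.1 flow chart was not used because its columns cannot be aligned reliably in the text copy. The end-of-treatment entry, "End of study treatment visit (D28 for cohort 1&2 or D84 for cohort 3", gives one draw per cohort, as do the +1 week and +4 week visits. Cohort 3 has two more: its Day 28 visit, and its Day 56 visit (5.3.5), which lists "Hematology and Biochemistry". The Cohort 2 list for Days 7, 14 and 21 contains no laboratory tests.

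| Cohort | Post-baseline laboratory days | Draws | On treatment |
|---|---|---|---|
| 1 (150 mg) | 28, 35, 56 | 3 | 1 |
| 2 (50 mg, HIV-uninfected) | 28, 35, 56 | 3 | 1 |
| 3 (50 mg, 84 days) | 28, 56, 84, 91, 112 | 5 | 3 |

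**Step 2. Cross-check against protocol Table 5.** From Day 1 on, each visit's volume range is 2.7 mL wide, which is the optional INR/PT tube.

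- Cohort 1 total: 493.0 − 482.2 = 10.8 mL = 4 × 2.7, so Day 1 plus 3.
- Cohort 3 total: 703.4 − 687.2 = 16.2 mL = 6 × 2.7, so Day 1 plus 5.
- Cohort 2: the rows sum to 344.2 to 355.0, again 10.8 mL and 4 draws. The printed total, 345.2 to 354.0, does not match its own rows.

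**Step 3. Conflicting text.** Protocol 5.4.3 asks for laboratory tests at every visit. Read literally, that raises only Cohort 2, to 6. SAP 11.4.2 names only screening and treatment-period visits; on that reading Cohorts 1 and 3 have 1 and 3 post-baseline draws. If Day 1 is included in the count, they have 4 and 6. Cohort 3 has more draws than Cohort 1 on every reading.

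**Step 4. Effect with independent draws.** Let p be the chance of an abnormal value at one draw, the same in every cohort. P(at least one in k draws) = 1 − (1 − p)^k. The values of p are assumptions.

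| p | k = 3 | k = 5 | Expected of 12 | Excess |
|---|---|---|---|---|
| 1% | 3.0% | 4.9% | 0.36 v 0.59 | 0.23 |
| 2% | 5.9% | 9.6% | 0.71 v 1.15 | 0.44 |
| 5% | 14.3% | 22.6% | 1.71 v 2.71 | 1.00 |
| 10% | 27.1% | 41.0% | 3.25 v 4.91 | 1.66 |
| 20% | 48.8% | 67.2% | 5.86 v 8.07 | 2.21 |

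**Step 5. Effect with correlated draws.** Abnormal values tend to persist within a subject, which shrinks the gap. A beta-binomial model with correlation r uses A = p(1 − r)/r and B = (1 − p)(1 − r)/r. P(none in k) is the product of (B + j)/(A + B + j) for j = 0 to k − 1. At p = 5% and r = 0.5, A = 0.05 and B = 0.95:

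- k = 3: 1 − 0.95 × 0.975 × 0.9833 = 8.9%.
- k = 5: 1 − 0.9108 × 0.9875 × 0.99 = 11.0%.

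The excess is 12 × 2.04% = 0.24 subjects. At p = 10% and r = 0.5 the shares are 17.4% and 21.0% (0.44 subjects). At r = 0.9 the ratio is about 1.05.

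**Step 6. The other measures in the same sentence.** By the visit lists, post-baseline vital signs are taken 3, 6 and 5 times in Cohorts 1, 2 and 3. At 5% with independence that gives 14.3%, 26.5% and 22.6%. ECG appears only at end of treatment and end of study after baseline, so it is balanced at 2 in each cohort.

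**Step 7. With matched draws.** At Day 28 every cohort has one draw after 28 days of dosing: 5% v 5%. Over end of treatment, +1 week and +4 weeks: 14.3% v 14.3%.

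**The case against.** Much of a like-for-like reading is already planned. Laboratory statistics are produced at each visit in separate cohort columns. A subject with a CS value at Day 28 enters the shift table by definition, so Day 28 CS shifts can be recovered in full whatever happens later. Safety also rests on adverse events and review of individual values, and CS abnormalities are recorded as adverse events. The study is descriptive, sequential and non-randomised, with 12 subjects per cohort. All of this stands, and it limits the importance of the point.

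It does not remove the point. The by-visit statistics are means, medians and ranges, not counts of abnormal values. In the shift table, non-clinically-significant (NCS) values appear only for subjects who also have a CS value, and meeting that condition again depends on the number of draws.

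A reader might go further and infer that the 50 mg count is inflated as such and hides a 150 mg effect. The documents do not support that, for four reasons:

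- Cohort 2 is also 50 mg, for the same 28 days and, by the visit lists, with the same 3 laboratory draws as Cohort 1. It is HIV-uninfected and not on antiretrovirals, so it is an imperfect comparator, but its laboratory count is not raised.
- Part of a higher Cohort 3 count may be a genuine effect of 84 days of treatment.
- Masking depends on assumed rates. With independent draws, 8.2% per draw at 150 mg would give the same expected count as 5% in Cohort 3, because 1 − 0.95^(5/3) = 8.2%. Nothing in the documents supports either rate.
- The rule excluding unscheduled results covers laboratory data only. For vital signs, SAP 11.4.3 plans only by-visit statistics, so it cannot be said that the schedule alone fixes what is counted.

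**Conclusion.** The point holds for one table. The whole-study count for Cohort 3 is not comparable with that for Cohort 1, because it mixes dose with two extra draws and a longer exposure. At an assumed 5% per draw the excess in Cohort 3 is about 0.25 subjects in 12 per parameter at correlation 0.5 and 1 subject with independent draws. At 10% with independence it is about 1.7. These figures assume equal per-draw risk in all cohorts, complete attendance and the draw counts from the visit lists. It is a moderate presentation flaw in a descriptive study: no test is invalidated, and the table is not the whole of the safety comparison by dose. The direction between Cohorts 1 and 3 is robust to the conflicting text on visits; the size is not known.

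**What to change.** In SAP 4.4 and 11.4.2, add for each laboratory parameter the number and percent of subjects with an abnormal value (NCS and CS) at Day 28, and name this as the between-cohort comparison. Day 28 is the scheduled laboratory visit at which every cohort has had equal exposure. Give separate counts at End of Rx, +1 week and +4 weeks. Keep the whole-study count and print the number of assessments beside it, for vital signs as well. Reconcile the every-visit wording in protocol 5.4.3 and the treatment-period wording in SAP 11.4.2 with the visit lists, so that the number of assessments is unambiguous.

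The cost is SAP text and one more table layout; no new data are needed. The Day 28 comparison does not use Cohort 3 values after Day 28, which are still reported separately. It is also fair rather than sensitive: at 5% only 0.6 of 12 subjects are expected to be abnormal. If the per-draw risk were 10% in Cohort 1 and 5% in Cohort 3, with independent draws, Cohort 1 would show the higher count with probability 52% at Day 28, against 51% on the whole-study count. The chance that the order is reversed falls from 31% to 18%.

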9.3.1. Clinical laboratory evaluation

Descriptive statistics for laboratory parameters will be computed at each scheduled assessment. If relevant for some parameter, change from baseline will also be tabulated.

In addition, shift tables from baseline will be presented.

9.4. Determination of Sample Size

No formal sample size calculations were performed. 36 subjects (24 HIV infected and 12 HIV uninfected subjects) are deemed sufficient to fulfil the study objectives.

10. STUDY CONDUCT CONSIDERATION

10.1. Regulatory and Ethical Considerations

10.1.1. General Requirements

The study will be conducted in compliance with the study protocol, ABIVAX Standard Operating Procedures and in accordance with any local regulatory requirements, to ensure adherence to Good Clinical Practice (GCP) as described in the following documents:

- ICH Harmonized Tripartite Guidelines for Good Clinical Practice 1996.
- US 21 Code of Federal Regulations dealing with clinical studies (including parts 50 and 56 concerning informed consent and IRB regulations).
- Directive 2001/20/EC on the approximation of the laws, regulations and administrative provisions of the Member States relating to the implementation of good clinical practice in the conduct of clinical studies on medicinal products for human use and its guidance.
- Declaration of Helsinki and its amendments.

Upon signing the protocol, the investigator agrees to adhere to the instructions and procedures described in it and thereby to adhere to the principles of Good Clinical Practice that it conforms to.

Written informed consents will be obtained for each subject before he or she can participate in the study.

ABIVAX will obtain favorable opinion/approval to conduct the study from the appropriate regulatory agencies in accordance with any applicable country-specific regulatory requirements prior to a site initiating the study in that country.

10.1.2. Independent Ethics Committee/Institutional Review Board

Prior to the start of the study, the study protocol and amendments if applicable as well as other appropriate study related documents will be submitted to an independent Institutional Review Board (IRB) or independent Ethics Committee (IEC), respectively.

For each center, it will be individually specified, who (investigator or sponsor) will be responsible for informing the IRB or IEC, respectively of any protocol amendments or new relevant information that require an ethical reconsideration of the study protocol.

If the investigator is responsible for obtaining approval, he/she should also obtain a statement from the IRB or IEC, respectively that it is organized and operates according to GCP and applicable laws and regulations.

10.1.3. Subject Informed Consent

It is the responsibility of the investigator to give each subject full and adequate verbal and written information regarding the aims, methods, anticipated benefits and potential hazards. The subject must be informed that participation is voluntary, and that they are free to withdraw from the study at any time without any disadvantages for their subsequent care. Although a subject is not obliged to give her/his reason(s) for withdrawing prematurely from the trial, the investigator should make a reasonable effort to ascertain the reason(s), while fully respecting the subject's rights. Written consent (signed and dated by the subject and the investigator) must be obtained prior to admission. The subject must be provided with a copy of the subject information and informed consent.

The data collected in this study will be processed anonymously at ABIVAX. Subjects should be informed about the purpose of the planned computer data processing and the publication of the data (e.g. at scientific meetings). The subject must give consent to the computer processing and to the publishing of anonymous data.

The subject must be informed of and consent in writing that personal data relating to the trial may be subject to audits by Health Authorities and the sponsor. However, personal data will be kept strictly confidential and will not be made publicly available.

10.1.4. Compensation to Subjects

Insurance coverage will be provided for all subjects enrolled in the study from the time of the subject's inclusion in the study (i.e. date of signing the ICF). The insurance coverage will be provided by the Sponsor and will be in line

with GCP guidance and legal requirements, but also in accordance with local regulations. Depending on the local policies and the services/availabilities of the insurance providers, different such providers may be used in individual countries. A confirmation of insurance and corresponding insurance conditions should be archived in the Investigator File.

11. STUDY MANAGEMENT

11.1. Remote Data Entry

An electronic case report form (eCRF) will be used to record all data required by the protocol. Remote Data Entry (RDE) will be used for data collection, i.e. the subject's information pertaining to the study, will be entered into the eCRF via a computer at the investigational site.

Prior to the start of the study, the investigator will complete a "*Delegation of significant study-related duties*" form, showing the signatures and initials of any person who is authorized to make or change entries in the eCRF and any person authorized to electronically sign the eCRF.

The eCRF used for this study is validated and fulfils the International Conference on Harmonization (ICH) Good Clinical Practice (GCP) requirements, European and FDA (21 CFR Part 11) regulations.

Training sessions will be held for all the Subjects who will use this tool (e.g. investigators, ABIVAX staff and contract research organization [CRO] staff, including project managers, CRAs and data managers).

Several supports are available to help all users with this tool including eCRF user manuals (CRA and site manuals) and five days a week / working hour's helpdesk (support line).

All of the information will be recorded through transcription from source documents into the eCRF by an authorized person.

The investigator is responsible for the management and accuracy of the information in the eCRF. At each monitoring visit, the subject medical files should be at the clinical research associate's (CRA) disposal for review.

